## 12.4 Statistical Methods

The primary analysis will compare the Pamidronate and Control groups according to LBMC measured by DXA using all available Day 360 measurements and adjusting for height, age, sex, Tanner score, and race. The analysis will be a multiple linear regression; the primary predictor will be randomized treatment assignment and adjusters listed above. If preliminary analysis shows that LBMC measurements have a grossly non-Gaussian (non- normal) distribution, a transformation of LBMC will be analyzed, most likely  $\log_{10}$  LBMC Secondary analyses will include the following:

- The hypothesis that subjects randomized to pamidronate will have higher total BMD, cortical BMD, trabecular BMD, and estimated bone strength measured by pQCT at 1 year compared to subjects randomized to control (Aim 1 Hypothesis 2) will be tested by applying the foregoing analyses to outcomes measured by pQCT, namely bone strength, total BMD, cortical BMD, and trabecular BMD, but excluding height from the adjusters.
- The hypothesis that cytokine levels will increase rapidly in the first 3 weeks after HCT, preceding an increase in markers of bone resorption (Aim 2 Hypothesis 1) will be tested, for each cytokine, by using all available data for each child (up to 4 measurements from Day -14 to Day 21) and fitting a mixed linear model with a random intercept and time trend for each child and testing whether the average time trend differs from zero.
- The hypothesis that in the Control Group, increased cytokine levels and receptor activator of nuclear factor- $\kappa$ B ligand/osteoprotegerin ratio at 3 weeks will be associated with decreased BMC and BMD at 1 year after HCT (Aim 2 Hypothesis 2) will be tested using linear regressions with dependent variables being each of the BMC and BMD measures at Day 360 and predictors being changes in each of the cytokine levels and RANKL/OPG ratio (from Day -14 to Day 21).
- For the hypothesis that markers of bone resorption will increase in the first 3 months after HCT, will remain elevated until at least Day 180 in the

Control Group, but will decrease after initiation of pamidronate at Day 90 (Aim 3 Hypothesis 1), the test of changes up to Day 90 will use the same type of analysis as for Aim 2 Hypothesis 1 but with up to 5 measurements (Day -14 to Day 90). Tests of changes after Day 90 will include all available data for each subject and use a mixed linear model to account for correlation of measurements within subject; changes over time will be tested separately in the Pamidronate and Control groups using contrasts and compared between groups by testing the interaction of group and measurement time (i.e., Day 180, Day 360).

For the hypothesis that markers of bone formation, including osteocalcin (OCN) will decrease in the first three months and in the Control Group lower OCN levels at Day 90 will be associated with lower BMC and BMD 1 year post-HCT (Aim 3 Hypothesis 2), the test of change in OCN to Day 90 will use all available data and the same type of analysis as for Aim 2 Hypothesis 1; the test of change from Day 90 to Day 360 will use control subjects only and simple linear regression with outcome each of the BMC and BMD measures at Day 360 and predictor OCN level at Day 90.

For analyses of Aims 2 and 3 and Aim 1 hypothesis 2, further secondary analyses will use multiple imputation to impute missing measurements. Finally, exploratory analyses will explore risk factors for bone loss, including sex, BMI percentile, LBM adjusted for height, calcium and vitamin D intake, CNS radiation, TBI vs. no TBI in conditioning regimen, donor stem cell source (cord blood vs. other), physical activity, and glucocorticoid exposure for prophylaxis or treatment of GVHD. Subjects who experience a bone fracture after HCT will be excluded from analyses of bone turnover markers but otherwise will be included in all analyses.

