## **1 Introduction, Background and Rationale**

Low bone mineral density (BMD) is common in children treated with hematopoietic cell transplantation (HCT) in both early and late follow-up (1-7). Low BMD in childhood is expected to increase the risk of early osteoporosis and increase the risk of fracture due to low peak bone mass (7-11). This has serious individual and societal implications due to impaired mobility and ability to participate in activities of daily living that occurs after fracture. In older adults, fracture has even been associated with an increased risk of death.

Bone health is dependent on a balance between bone resorption and bone formation; when this balance is disrupted bone loss and ultimately osteoporosis develop. BMD decreases in the first 6 months after HCT (1). A recent study has shown that bone resorption is significantly increased by 100 days after pediatric HCT and remains elevated through at least 180 days after HCT (12), which offers an opportunity for intervention.

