### **6.2 Randomization (Day 90 Post-HCT Visit +/- 14 days)**

Randomization to pamidronate (Pamidronate Group) or no pamidronate (Control Group) will occur at Day 90 (+/- 14 days) by the institutional study coordinator based on the randomization schedule developed by the study statistician and entered into OnCore.

A brief review of continuing eligibility will be done and subjects will not be eligible for randomization if one or more of the following are true:

- Vitamin D ( $D_2+D_3$ )  $<20$  ng/ml as use of pamidronate is contraindicated due to potentially higher risk of hypocalcemia. Levels should be measured within 14 days prior to randomization.\*\*†
- serum creatinine is  $> 2$  times the baseline value (at Study Entry) - perform within 14 days prior to randomization
- an investigational study drug or agent, including biphosphonates, Denosumab, or Teriparatide, was administered within the previous 4 weeks or is planned for use during study participation (Day 90 through Day 360)
- positive pregnancy test (performed within 14 days prior to randomization)
- Inability to successfully complete a DEXA scan
- the parent or adult patient refuse randomization
- disease relapse has occurred

The randomization will be stratified by age with 2 strata:  $< 10$  years old and  $\geq 10$  years old.

If the patient is ineligible for or refuses randomization, no further research related procedures or treatment will occur after the Day 90 visit; however permission to continue review of the patient's medical record through the Day 360 visit for routine clinical information is embedded within the consent form document. This information will be collected only if the patient continues care at the enrolling

institution. Patient care will be at the discretion of the treating physician(s) and independent of this study.

OnCore will automatically generate an email alerting key study personnel of the randomization (or lack of).

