**7.4 Pamidronate**

**7.4.1 Treatment Plan**

Subjects randomized to the Pamidronate Group will receive 3 single doses of pamidronate at 3-month intervals (Day 90 +/-14 days, Day 180 +/-14 days, and Day 270 +/-30 days).

Note: All time point specific laboratory testing procedures (sections 8.1 and 8.3) must be collected prior to the pamidronate infusion (except those specifically designated post infusion); however for ease of scheduling the consultations as well as the Day 90 DXA and Day 90 pQCT may be performed after the infusion as long as done within the +/-14 day window. Ionized calcium or corrected calcium, and Vitamin D levels (D2+D3) will be drawn prior to pamidronate infusions. If either are low, the subject should receive supplemental calcium and/or Vitamin D per Section 7.3. If the subject is receiving supplemental calcium, an ionized or corrected calcium level should be drawn after the pamidronate infusion end but prior to discharge from clinic on the day of the pamidronate.

Prior to each infusion the patient will be assessed and pamidronate will be held if:

- Serum creatinine is > 2 times the baseline (Study Entry) level – refer to section 7.3.2 for monitoring plan – the pre-treatment creatinine may be done anytime within 72 hours prior to the planned pamidronate administration

- Pregnancy test is positive (subject will permanently discontinue study drug) per section 7.3.5 – pregnancy testing may be done anytime within 72 hours prior to the planned pamidronate administration

Pamidronate 1 mg/kg (to a max dose of 60 mg) will be administered via a single IV infusion over 4 hours using a line separate from all other drugs. Dosing will be based on the patient's actual weight or, if overweight, on ideal body weight (IBW). This will be followed by a normal saline flush of 20 cc total given at the same rate as the pamidronate.

Premedication: Subjects will be given 15 mg/kg acetaminophen (or maximum of 500 mg) prior to pamidronate infusion then every 4 hours as needed for a maximum of 24 hours.

Post-Pamidronate Infusion Laboratory Tests: A serum calcium level will be done after the pamidronate infusion end but prior to discharge from clinic on the day of the pamidronate.

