## 8 Study Related Tests and Procedures

### 8.1 Schedule of Tests and Procedures

	Screen a	Study Entry b	Day 0	Day 7 (±2)	Day 14 (+ 2)	Day 21 (±2)	Day 90 (±14)	Day 180 (±14)	Day 270 (±30)	Day 360 (±30)
Informed Consent / Assent	X or X									
Physical Examination	X c or X c									X c
Weight	X	X					X	X	X	X
Height		X								X
Medical History	X or X						X	X	X	X
Medication Usage	X or X					X	X	X	X	X
Creatinine	X or X						X	X	X	
Urine or serum Pregnancy Test d,e	X or X						X	X f	X f	X
Diet & Activity Questionnaire		X					X	X	X	X
Adverse Event Assessment							X	X	X	X
Ionized/ or corrected Calcium	X or X						X f	X f	X f	
Vitamin D (D 2 +D 3 )	X or X						X g	X	X	X
iPTH		X					X			X
CTX, P1NP, & OCN		X		X	X	X	X	X		X
Urinary DPD and Creatinine		X		X	X	X	X	X		X
RANKL & OPG		X		X	X	X	X			
IL-6, IL-7, & TNF- $\alpha$		X		X	X	X	X			
DXA h		X					X			X
pQCT i							X			X
HCT			X							
Vitamin D & Calcium Administration j			X-----							X
Randomization – refer to section 6.2							X			
Pamidronate Administration k							X	X	X	
End of infusion (same day) serum calcium							X l	X l	X l	
Post infusion (next a.m.) m serum creatinine and spot urine for albumin and creatinine							X l	X l	X l	
Adverse event assessment by telephone 1 week post infusion (+/-3 days)							X l	X l	X l	

CTX = carboxy-terminal collagen crosslinks; DXA = dual-energy x-ray absorptiometry; DPD = deoxypyridinoline; HCT = hematopoietic cell transplantation; IL = interleukin; iPTH = intact parathyroid hormone; OCN = osteocalcin; OPG =

osteoprotegerin; P1NP = procollagen type 1 amino-terminal propeptide; pQCT = peripheral quantitative computed tomography; RANKL = receptor activator of nuclear factor- $\kappa$  B ligand; TNF- $\alpha$  = tumor necrosis factor alpha.

a Screening will occur during the pre-HCT work-up.

b Evaluations and tests only in the Study entry column are performed only after consent is signed and must be completed within 4 weeks (6 weeks for DEXA) prior to beginning pre-HCT conditioning regimen. If DEXA cannot be completed prior to conditioning, this will not be considered a protocol deviation

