### **8.2.4 DXA and pQCT**

Subjects will have DXA scans of L1-L4 and total body with body composition performed at the time points specified in Section 8.1 to compare BMC and body composition before and after study treatment. For the DXA scan, at least 2 vertebrae are required (i.e. L3-L4) and the same 2 vertebrae must be included on all follow-up exams.

If results from the DXA image suggest a compression fracture, the study PI or coordinator will confirm that the participant's primary care team knows of the results and appropriate follow-up (i.e. lumbar spine x-ray) is done. Note that there is no need to repeat an x-ray if (1) one was performed within the previous 12 months for the evaluation of the same vertebra with the highest BMD Z-score, and (2) was negative for fracture.

For subjects enrolled at the UMN, pQCT of the left tibia and non-dominant radius

will also be performed at the time points specified in Section 8.1.

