## 12.3 Randomization Scheme

The randomization will be stratified by age with 2 strata, < 10 years old and  $\geq$  10 years old, with 2/3 of the planned enrollment in the < 10 stratum. These fractions roughly reflect the proportion of each age group in the target study population. This choice of age groups is also based on our recent data which patients <10 years are more likely to be more severely affected (51). Each site's randomization schedule will use permuted blocks of lengths 2 and 4 within each stratum, so the study groups at a site never differ in sample size by more than 2 patients in

each stratum. The block lengths of 2 and 4 are alternated at random to make it harder to predict future treatment assignments. Randomized treatment assignments will be issued on Day 90 using a method that conceals the assignment until it is issued.

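### A cheap improvement, not an error: the primary LBMC model leaves out each child's own earlier LBMC, which is already scheduled, and site, which is blocked in the randomisation

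*Combined protocol and SAP*

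**What the plan says.** - **Model (12.4).** The primary analysis is a multiple linear regression of Day 360 LBMC on randomised arm, "using all available Day 360 measurements and adjusting for height, age, sex, Tanner score, and race". The same adjusters define the endpoint and hypothesis (Study Summary, 3.1, 11.1) and the planning SD (12.1). No treatment comparison in section 12 names an earlier LBMC or site.
- **Scans (8.1, 8.2.4).** DXA is scheduled at Study Entry, Day 90 and Day 360. Its stated purpose is "to compare BMC and body composition before and after study treatment". At least two vertebrae are needed, and "the same 2 vertebrae must be included on all follow-up exams".
- **Randomisation (12.3).** Each site has its own blocked schedule within age stratum, so that "the study groups at a site never differ in sample size by more than 2 patients" in a stratum. Age is in the model; site is not.
- **Limits on a baseline scan.** Section 7.4.1 says the "Day 90 DXA and Day 90 pQCT may be performed after the infusion". Section 6.2 bars randomisation for "Inability to successfully complete a DEXA scan", but gives that check no date. For the Study Entry scan, a footnote to 8.1 says: "If DEXA cannot be completed prior to conditioning, this will not be considered a protocol deviation".
- **Bone loss in between (section 1).** "BMD decreases in the first 6 months after HCT", so the two earlier scans are not interchangeable.

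**The concern.** A child's own earlier bone mass is a natural candidate to predict later bone mass, and the trial collects it. If it predicts Day 360 LBMC beyond the five listed covariates, the planned confidence interval is wider than the data allow. The estimate also moves with whatever difference in starting bone mass chance produces between arms.

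The stake is precision. Section 12.1 expects 192 children to be screened to yield 60 evaluable, so extra children are expensive and a model term is not.

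Site is the smaller matter. The design balances on it, and the usual practice is to carry such a factor into the model.

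**Working it through.** **Inputs.** From 12.1: 30 per arm and a 0.75 SD difference, where the SD is after the five covariates and equals 2.5-4 g. Not in the documents and therefore assumed: two-sided alpha 0.05; rho from 0 to 0.7, where rho is the partial correlation of earlier with Day 360 LBMC given the five covariates; and the share of children whose baseline must fall back to Study Entry.

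**1. The plan's own figure.** Non-central t with df = 60 - 2 - 5 = 53 (Tanner and race as one column each) and non-centrality 0.75 × √(30/2) = 2.905 gives 81.4%, against 80% stated. The stated detectable difference of 2-3 g also agrees: 0.75 × 2.5 = 1.9 g and 0.75 × 4 = 3.0 g.

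**2. Formula with baseline and site.** df = 51; non-centrality = 2.905 / √(1 - rho²). The difference detectable at 80% power falls from 0.74 SD to 0.72, 0.70, 0.64 and 0.53 SD at rho 0.2, 0.3, 0.5 and 0.7.

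**3. Simulation.** The formula ignores chance imbalance in the covariates, so trials of 60 children were simulated with arms equal within site and age stratum and two thirds of children under 10. There were 60,000 trials with no fallback and 40,000 per setting with fallback.

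The fallback runs assume that 30% of children in both arms use Study Entry. That scan correlates 0.7 × rho with Day 360 and 0.7 with Day 90, and its mean is 0.5 SD higher. One in five of those falling back has no Study Entry scan (0.30 × 0.20 = 6% of all children), and the value is imputed without using arm. The model has a term for which scan supplied the baseline.

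| | Formula, no fallback | Simulation, no fallback | Simulation, 30% fallback |
|---|---|---|---|
| Planned model | 81.4% | 78.3% | 78.0-78.3% |
| Both terms, rho 0 | 81.3% | 77.4% | 76.4% |
| rho 0.2 | 82.9% | 79.0% | 77.7% |
| rho 0.3 | 84.8% | 81.1% | 79.3% |
| rho 0.5 | 90.8% | 87.8% | 85.1% |
| rho 0.7 | 97.9% | 96.6% | 93.0% |

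The last column describes the recommended rule. Its break-even, by interpolation, lies between 0.2 + 0.1 × (78.0 - 77.7)/(79.3 - 77.7) and 0.2 + 0.1 × (78.3 - 77.7)/(79.3 - 77.7), that is about 0.22 to 0.24. With no fallback it is about 0.15. Type I error was 4.9-5.2% throughout, and bias under the recommended rule was at most 0.0023 SD.

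**4. Higher fallback.** At 60% fallback, power is 78.6% at rho 0.3 and 82.9% at rho 0.5. At 90% it is about 78% and 82-83%. Planned power in those runs was 78-79%.

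**5. Chance imbalance.** The baseline difference between arms, given the covariates, has standard error √(2/30) = 0.26 SD. A one-standard-error imbalance moves the planned estimate by 0.26 × rho: 0.08, 0.13 or 0.18 SD at rho 0.3, 0.5 or 0.7.

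**6. Site alone.** Suppose the sites differ by s within-site SDs in adjusted LBMC. Leaving site out inflates the estimated SD by √(1 + s²/4), while blocking keeps the arms balanced. By normal approximation, type I error is 4.3% and power 81% at s = 0.5, and 2.8% and 76% at s = 1. With site in the model, power is 81.3%. Omission therefore makes the test conservative, and it costs little unless the sites differ greatly.

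**7. Why the baseline rule must be the same in both arms.** Only one arm has an infusion. A rule that takes the Day 90 scan if it precedes the infusion, and otherwise Study Entry, sends only pamidronate children to the higher, pre-transplant value. Under the same assumptions at rho 0.5, with no term for scan source, the bias is about 0.04 SD if Study Entry is 0.25 SD higher and about 0.07 SD if it is 0.5 SD higher.

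**The case against.** The strongest reply is that this is a preference. The planned model is valid, matches the SD used for planning, and reaches its stated power. Section 12.1 expects race and height to halve the age- and sex-adjusted SD, so much of the variation between children is already removed. The planned confidence interval already allows for chance imbalance. The gain rests on a correlation and a fallback share that the documents do not give, and at rho 0.2 with 30% fallback there is a slight loss. If most children fell back to Study Entry, the gain would be small unless rho were about 0.5 or more. All of that stands, and it is why this is an improvement and not a defect.

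Two considerations limit it. The worst simulated loss is 1 to 2 points of power, against a gain of about 7 points at rho 0.5 with 30% fallback (85.1% against about 78%). The DXA bar in 6.2 may also keep fallback low, although without a date it does not settle the matter.

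A reader might infer more than the documents support:

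- **That the analysis is biased or underpowered without a baseline.** It is neither: randomisation protects the comparison and the stated power reproduces.
- **That 8.2.4 commits the trial to an analysis of change which section 12 breaks.** It states why the scans are taken and specifies no model.
- **That power of 91% or 98% is available.** Those formula values need rho of 0.5 or 0.7, no fallback, and no chance imbalance in covariates.

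**Conclusion.** The omission is confirmed and worth correcting as an inexpensive gain in precision. Under the recommended rule with 30% fallback, power runs from about 76% at rho 0 to 93% at rho 0.7, against about 78% planned. It pays once rho exceeds about 0.2 to 0.25. Nearly all the gain comes from baseline LBMC; site adds little and mainly makes the model match the design.

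These figures rest on assumed values of rho, the fallback share, how well Study Entry stands in for Day 90, and two-sided alpha 0.05. No figure is claimed for TBMC or pQCT. Simply adding Day 90 LBMC would not be safe, because 7.4.1 allows that scan to follow treatment.

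**What to change.** In 12.4:

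- Add baseline LBMC and site to the adjusters, with baseline on the outcome's scale (log10 if LBMC is transformed). Use the same form for TBMC.
- Define baseline identically in both arms as the last DXA at or before randomisation: Day 90 if it qualifies, otherwise Study Entry. Add a scan-source term if both are used. Never use a later scan as baseline.
- Impute a missing baseline once from pre-randomisation covariates without using arm, and keep every randomised child with a Day 360 scan. Do not use a missing-value indicator for scans set aside because they followed the infusion.
- Compute baseline and Day 360 LBMC over the same vertebrae. A scan may hold as few as two, and content in grams depends on how many are summed.
- Fix the model before any outcome by arm is seen, since the trial is open-label.
- State how this carries to pQCT, which 12.4 analyses in the same way. It is done at one site only, so site drops out; a baseline value should enter only under the same timing rule.

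Elsewhere, make matching edits where the adjuster list is repeated (Study Summary objectives, 3.1, 3.2, 11.1, 11.2, 12.1). Align the t-test in the Study Summary with the regression in 12.4. Reconcile 6.2 and 7.4.1 on when the Day 90 scan is done relative to randomisation, since that decides how many children fall back.

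**Cost.** Two or three model terms, and a protocol amendment with IRB approval and possibly FDA notification (13.5). If the terms predict nothing, simulated power falls by 0.9 point with no fallback (78.3% to 77.4%) or 1.9 points with 30% fallback (78.3% to 76.4%). No new data are collected.

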Correlative Objectives:	
 
• Cytokine levels will increase rapidly in the first 3 weeks after HCT, preceding an increase in markers of bone resorption.
 
• In the Control Group, increased cytokine levels and receptor activator of nuclear factor-<math>\kappa</math> B ligand (RANKL)/osteoprogenin (OPG) ratio 3 weeks post-HCT will be associated with decreased BMC and BMD at 1 year post HCT.
 
• Markers of bone resorption will increase in the first three months after HCT, will remain elevated until at least Day 180 in the Control Group, but will decrease after initiation of pamidronate at Day 90 in the Pamidronate Group.
 
• Markers of bone formation, including osteocalcin (OCN) will decrease in the first three months after HCT and in the Control Group lower OCN levels at Day 90 will be associated with lower BMC and BMD 1 year post-HCT.
 

Duration of Study Participation	1 year from HCT
Number of Subjects	60 evaluable patients (30 per site) over 3.5 years

Main Inclusion Criteria	Subjects will be $\geq 1$ and $\leq 20$ years of age at the time of enrollment and receiving an allogeneic HCT for a hematologic malignancy in complete remission and using a myeloablative preparative regimen, non-malignant diseases with a myeloablative or non-myeloablative preparative regimen, or severe aplastic anemia (SAA) for which any conditioning therapy is permitted.
Standard Therapy	All Subjects - Standard supplementation with calcium and vitamin D beginning at admission to the hospital (prior to HCT) and continuing until post-HCT Day 360 visit
Study Product, Dose, Route, Regimen	Pamidronate Group Only Pamidronate disodium single 1 mg/kg intravenous infusion administered every 3 months for 3 doses - post-HCT Days 90, 180 and 270.
Endpoints	The primary study endpoint is lumbar bone mineral content (LBMC).  Other endpoints are TBMC (excluding head), bone strength, total BMD, cortical BMD, trabecular BMD, levels of markers of bone turnover, cytokines, RANKL/OPG ratio, and body composition.
Statistical Methods	The primary analysis will compare the Pamidronate and Control Groups according to LBMC measured by DXA using a t-test applied to all available Day 360 measurements. A secondary analysis will use multiple imputation to impute Day 360 BMC and BMD measurements for each subject who does not provide one.

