c Including Tanner staging of pubertal development.

d Females >10 years only.

e If documentation of a negative pregnancy test within 7 days prior to DXA scan is available, the pregnancy test does not need to be repeated.

f If result is below the lower limit of normal refer to section 7.2 and 7.3.

g Subjects who have vitamin D levels ( $D_2+D_3$ ) <20 ng/ml at Day 90 will not be eligible for randomization per section 6.2.

h L1-L4 and total body scans with body composition.

i Subjects at the University of Minnesota (UMN) only.

j All subjects will begin taking supplemental vitamin D per day and calcium, if needed, to meet recommended dietary allowance (RDA) requirement upon admission to the hospital for the HCT and continue through Day 360. If a subject has low vitamin D ( $D_2+D_3$ ), dietary calcium intake is below RDA, or the ionized/or corrected calcium level is below the normal range, additional vitamin D and/or calcium supplementation will be given per Section 7.3.

k For subjects randomized to the Pamidronate Group, 1 mg/kg (60 mg max) will be administered via intravenous (IV) infusion over 4 hours. Subjects will be given 15 mg/kg acetaminophen (or maximum of 500 mg) prior to infusion then every 4 hours as needed for a maximum of 24 hours. Postmenarchal subjects randomized to pamidronate will be put on an oral contraceptive pill (Loestrin or Orthocept or other OCP that contains 30 mcg ethinyl estradiol), birth control patch or other effective method of birth control. The results of the serum creatinine and pregnancy test (if applicable) must be reviewed before drug administration.

l Pamidronate patients only

m Serum creatinine level and spot urine collected the morning after each pamidronate infusion; however if not feasible at that time may be done anytime within 7 days after pamidronate infusion. A morning collection is preferred, but not mandatory. The time of the urine collection must be recorded.

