### **11.2 Secondary Clinical Endpoints**

Other endpoints are:

- TBMC measured by DXA (adjusted for height, age, sex, Tanner stage and race).
- Estimated bone strength, total BMD, cortical BMD, and trabecular BMD of the left tibia and non-dominant radius measured by pQCT.
- Levels of markers of bone resorption (carboxy-terminal collagen crosslinks [CTX] and deoxypyridinoline [DPD]), and bone formation (procollagen type 1 N-terminal propeptide [P1NP] and OCN)
- RANKL, OPG, and RANKL/OPG ratio.
- Levels of cytokines including interleukin (IL)-6, IL-7, and tumor necrosis factor-alpha (TNF- $\alpha$ ).
- Body composition: body mass index (BMI) percentile, lean body mass, and body fat mass (from DXA) adjusted for height.

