## **12 Statistical Considerations**

### **12.1 Sample Size**

Sixty (60) subjects total (30 each in the Control and Pamidronate groups) gives 80% power to detect a difference between groups of 0.75 standard deviations (SDs)

describing variation in LBMC within study group after adjusting for height, age, sex, Tanner score, and race. Adjusting for age and sex, this SD is 5-8g (46, 47); adjusting further for race and height should reduce this SD by about half (48-50). This gives a within-group SD of about 2.5-4g and a detectable difference of 2-3g. To have 60 evaluable subjects, 192 need to be screened to allow for a 50% consent rate, 10% death rate by Day 90, 20% death rate between Day 90 and Day 360, and 10% drop out after randomization.

Anticipated Enrollment Over Duration of Study

	Screen	Study Entry Day -14 a	Day 7	Day 14	Day 21	Day 90	Day 180	Day 270	Day 360
Total	192	96	96	96	96	86	86	86	60
University of Minnesota (UMN)	96	48	48	48	48	43	43	43	30
Fred Hutchinson Cancer Research Center	96	48	48	48	48	43	43	43	30
a Day 0 is the day of hematopoietic cell transplantation (HCT).									

According to data from 2011 to 2012, 36 allogeneic transplants have been performed at UMN and 37 have been performed at Fred Hutchinson Cancer Research Center. It is expected that screening 28 patients per year will be feasible for both sites.

It anticipated that enrollment will take 3.5 years.

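### Section 12.4 drops height from the model for estimated bone strength as well as for the BMD outcomes, which can cost precision in a comparison of about 15 children per arm

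*Combined protocol and SAP*

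**What the plan says.** The primary LBMC model in section 12.4 is a multiple linear regression "using all available Day 360 measurements and adjusting for height, age, sex, Tanner score, and race", with randomized arm as the main predictor. The same section carries that model over to the pQCT outcomes, "namely bone strength, total BMD, cortical BMD, and trabecular BMD, but excluding height from the adjusters". This leaves age, sex, Tanner score and race. No reason is given for removing height, bone strength is not treated separately, and no other section restores height for it.

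Section 11.2 lists the endpoints as "Estimated bone strength, total BMD, cortical BMD, and trabecular BMD of the left tibia and non-dominant radius measured by pQCT" and does not say which strength index is meant. The same list adjusts TBMC, lean mass and fat mass for height, and section 11.1 does so for LBMC. On the value of that adjustment for LBMC, section 12.1 says that "adjusting further for race and height should reduce this SD by about half".

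Footnote i to the schedule in section 8.1 limits pQCT: "Subjects at the University of Minnesota (UMN) only". The Study Summary plans "60 evaluable patients (30 per site) over 3.5 years", and the UMN row of the enrollment table in section 12.1 ends at 30. Section 8.2.3 schedules height at study entry and at Day 360 only.

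**The concern.** A volumetric density is mineral per unit volume, so omitting height from its model is a reasonable choice. A strength index normally combines density with cross-sectional geometry and so grows with the bone. Section 12.4 treats the two kinds of outcome alike, although the plan elsewhere adjusts outcomes that scale with body size for height.

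If height explains variation in strength beyond age, sex, Tanner score and race, leaving it out puts that variation into the residual. Enrollment runs from 1 to 20 years of age and randomization is stratified by age but not by height. Bone strength belongs to a named secondary hypothesis (section 3.2). With about 15 children per arm, that comparison has little precision to spare.

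**Working it through.** **Reproducing the plan's own figures.** Section 12.1 claims 80% power for 0.75 SD with 30 per arm. It states no alpha, so I assume two-sided 0.05. The noncentral t gives 81.5% (81.4% after removing 5 covariate degrees of freedom), which agrees. Attrition also reproduces: 192 × 0.5 = 96; 96 × 0.9 = 86.4; 86.4 × (1 − 0.20 − 0.10) = 60.5. Half of 60 is 30 at UMN, or about 15 per arm under 1:1 allocation. The plan gives no power figure for pQCT.

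**Strength model as written (no height).** The inputs are n = 15 per arm and four covariates at one parameter each, so df = 30 − 2 − 4 = 24. The noncentrality is λ = d√(n/2) = 2.739d, with d in units of the residual SD after age, sex, Tanner score and race.
- Power at d = 0.75, the plan's primary effect size, is 50%.
- The difference detectable with 80% power is d = 1.066 (λ = 2.92, critical t = 2.064).

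**Adding height.** Two things change.
- The residual variance is multiplied by 1 − r², where r is the partial correlation of height with strength given the other four covariates.
- An extra covariate has a price at N = 30. Treating covariates as random, the variance of the treatment estimate carries the factor (N − 3)/(N − k − 3). Going from k = 4 to k = 5 moves it from 27/23 to 27/22, a ratio of 23/22 = 1.045. In addition, df falls from 24 to 23 (critical t = 2.069).

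The net variance ratio is therefore V = (1 − r²) × 23/22. Power is evaluated at 1.066/√V on 23 df. The detectable difference, in the same SD units, is 1.068 × √V, where 1.068 is the 80% value on 23 df.

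| r (assumed) | V | 1.066/√V | Power | Detectable difference |
|---|---|---|---|---|
| 0 | 1.045 | 1.04 | 78% | 1.09 SD |
| 0.2 | 1.004 | 1.06 | 80% | 1.07 SD |
| 0.3 | 0.951 | 1.09 | 82% | 1.04 SD |
| 0.5 | 0.784 | 1.20 | 88% | 0.95 SD |
| 0.7 | 0.533 | 1.46 | 97% | 0.78 SD |

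The model without height gives 80% and 1.07 SD. Break-even is at V = 1, so r² = 1/23 = 4.3% and r is about 0.21.

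**Sensitivity.** Coding Tanner stage or race with more than one parameter hardly matters for degrees of freedom: with seven covariate parameters the detectable difference is 1.073 SD instead of 1.067.

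**The case against.** The case for leaving 12.4 alone has real substance.

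- **The premise comes from outside the documents.** They never define the strength index, so its dependence on bone size is technical knowledge rather than something the plan says. This stands, and it is a reason to name the index.
- **The size of the benefit is unknown.** No correlation of height with strength is given, and age, sex, Tanner score and race already capture part of body size. A reader might infer from section 12.1 that the SD for strength would also halve. The documents do not support this: that statement concerns LBMC, credits race and height jointly, and starts from a model with age and sex only. The pQCT model already contains race and Tanner score.
- **There is no bias to repair.** A reader might infer that a chance height imbalance between two small arms would produce a false strength effect. Treatment is randomized, so the comparison without height is unbiased and its type I error is controlled. Chance imbalance is already part of the standard error.
- **Which height matters.** Day 360 height is measured about nine months after randomization, and adjusting for it means conditioning on a post-randomization value. This objection stands and decides the form of the fix. Study-entry height may correlate less closely with Day 360 strength, which is one more reason not to lean on the upper end of the range.
- **The outcome is secondary**, measured at one site, with no power claimed for it. This limits the importance of the point but does not remove it.

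**Conclusion.** The point holds as a question of precision on one secondary outcome. Height is excluded for estimated bone strength without a stated reason, while the plan's other size-dependent outcomes keep it. Adding height would change power at 1.07 SD by nothing worth having at r = 0.2, and by about 2, 8 and 17 percentage points at r = 0.3, 0.5 and 0.7. If height were unrelated to strength given the other covariates, the cost would be about 2 points.

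These figures rest on 15 evaluable children per arm, two-sided 0.05, one parameter per covariate and an assumed r, so they are a range and not an estimate. The exclusion of height for total, cortical and trabecular BMD is not in question, and the primary LBMC conclusion is unaffected.

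**What to change.** Amend the pQCT bullet in section 12.4 before the data are analysed, along these lines: *Height is omitted from the models for total, cortical and trabecular BMD only; the model for estimated bone strength also includes height at study entry.* In the same edit, name the strength index in sections 11.2 and 12.4.

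Study-entry height is the only height that section 8.2.3 schedules before randomization. Name it explicitly: a bare reference to the LBMC model would not settle the matter, because section 12.4 does not say which height that model uses.

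The cost is one clause and one degree of freedom, with no new data. The downside is a negligible loss of precision if r is below about 0.2.
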